## 11 Data Handling and Record Keeping

### 11.1 Confidentiality

All research related records initiated as a result of a subject's participation in this study that reveal the subject's identity will remain confidential except as may be required by law. Data obtained from this study will not identify the subjects individually. Subjects will be assigned code names and ID numbers. Biospecimens will be stored securely in a locked room only accessible to study staff. Data obtained from our studies may be published, but published data will not identify individual participants. Original research-related records may be reviewed by the Boston Medical Center Institutional Review Board and regulatory authorities for the purpose of verifying clinical trial procedures and/or data. Information will be held and processed on a computer, but access to these computerized records will be password protected and restricted to study staff. At the onset of an initial clinical encounter, subjects will be informed of Federal privacy guidelines that pertain to them under the Healthcare Insurance Portability and Accountability Act. Results of urine drug or pregnancy testing will not become part of the subject's medical record. Subjects will only be contacted regarding future studies if they indicate that they are

interested in being contacted by initialing in the specific section of the consent form. Information may be held and processed on a computer. Access to these computerized records will be password protected and restricted to study staff.

Data Use Agreements and Material Transfer agreements will be filed with the appropriate offices regarding receiving identified data and biospecimens from Massachusetts General Hospital.

## 11.2 Source Documents

Structured diagnostic and psychosocial interviews will be collected from youth and parents when available. Biological samples of blood will be collected to measure hepatic function, test for hepatitis C and HIV, and monitor glucose and lipid levels during treatment. Urine samples will be collected to measure drug toxicology and detect pregnancy. For a full list of data records, please see the Schedule of Events in the Appendix.

Data generated by the methods described in the protocol will be recorded in the subjects' medical records and/or special research files, one per subjects, which will be identified by an ID number that will not identify the subject in any way. Data may be transcribed legibly on hard copy CRFs supplied for each subject or directly inputted into REDCap—an electronic data management system. Any hard copy material including the names of subjects or other identifying information (consent/assent forms, paper records) will be kept in locked filing cabinets in a locked room or scanned and uploaded to a password-encrypted folder on the BMC secure network. Documentation linking subjects' names and numbers will be kept in a password-protected electronic file on a BMC networked drive only accessible by the project coordinator and primary investigator (PI) on a password-protected computer located behind a secure and maintained firewall. Blood sample collection, analysis and disposal will be managed by the BMC lab. Urine sample collection, analysis, and disposal will be managed by study staff and samples will not contain identifying information. Data will be transmitted only in pooled form, and subjects will be identified by ID numbers. Any publications of study findings will be reported so that no person can be identified individually. These issues will be clearly stated in consent forms and discussed with participants during the informed consent process, prior to any study related procedures.

## 11.3 Case Report Forms

The study case report forms (CRF) will be the primary data collection instruments for the study. All data requested on the CRFs will be recorded. All missing data will be explained. If a space on the CRF is left blank because the procedure was not done or the question was not asked, "N/D" will be written. If the item is not applicable to the individual case, "N/A" will be written. All entries will be printed legibly in black ink. If any entry error has been made, to correct such an error, a single straight line will be drawn through the incorrect entry and the correct data will be entered above it. All such changes will be

initialed and dated. There will be no erasures or white-out on CRFs. For clarification of illegible or uncertain entries, the clarification will be printed above the item, then initialed and dated.

See the Appendix for the following CRFs:

Clinician rated assessments (stored in patient files/ REDCap):

- Mini-International Neuropsychiatric Interview (M.I.N.I. 7.0)
- DMS-V Kiddie Schedule for Affective Disorders and Schizophrenia Present and Lifetime (KSADS-PL) module for DMDD
- Weiss Adherence Interview
- Adverse Experiences and Concomitant Medications
- Young Mania Rating Scale (YMRS)
- Abnormal Involuntary Movement Scale (AIMS)
- Clinical Global Impressions (CGI)[62] scale for SUD and SMD
- Columbia Suicide Severity Rating Scale (C-SSRS)
- DSM-V Global Assessment of Functioning (GAF) scale
- Reproductive Potential Form

Subject/Parent rated scales (stored in patient files/REDCap):

- Socioeconomic Status/Background
- Youth Self-Report (YSR) and Adult Self-Report (ASR)
- Behavior Rating Inventory of Executive Function (BRIEF)
- Beck Depression Inventory-II (BDI-II)
- Patient Health Questionnaire-9 (PHQ-9)
- Weiss Craving Scale
- Fagerström Tolerance Questionnaire for Adolescents
- Timeline Followback of Substance Use (TLFB)
- Risk Behavior Survey
- Supplemental Substance Use Questionnaire

Other CRFs (stored in patient files/REDCap):

- Laboratory tests: Drug screen (urine and breathalyzer), Urine HCG

- Safety/reliability procedures: EKG, Heart Rate, Blood Pressure, Height, Weight
- Chart Note
- Adverse Events Log
- Concomitant Medication Log
- COVID-19 Screening Questions

Other CRFs stored in patient Medical Record and patient files/REDCap

- Laboratory tests: AST/ALT, Hepatitis C, HIV, Fasting Lipids, Fasting Glucose, Urine THC, Creatinine

#### 11.4 Study Records Retention

All study records will be retained for at least seven years after the completion of the study, per Boston Medical Center Research Center requirements. These records include informed consent documents for all subjects.

### 12 Statistical Plan

#### 12.1 Study Hypotheses

**Primary Aim 1: Evaluate the effect of quetiapine on SUD.** Hypothesis 1A: Treatment with quetiapine will decrease self-reported substance use for primary substance of use (e.g. number of days of use past month, % abstinence past month). Hypothesis 1B: Treatment with quetiapine will increase number of toxicology specimens negative for primary substance of use Hypothesis 1C: Treatment with quetiapine will decrease drug craving for primary substance of use.

**Primary Aim 2: Evaluate the effect of quetiapine on SMD.** Hypothesis 2A: Treatment with quetiapine will result in a decrease in symptoms of mania demonstrated by reduction in Young Mania Rating Scale. Hypothesis 2B: Treatment with quetiapine will result in a decrease in symptoms of depression demonstrated by reduction in the Beck Depression Inventory II.

**Primary Aim 3: Evaluate the effect of quetiapine on engagement in outpatient treatment.** Hypothesis 3A: Treatment with quetiapine will lead to greater engagement in outpatient treatment as demonstrated by greater number of appointments attended in the active treatment group.

#### 12.2 Sample Size Determination

Since there have not been any published studies to date on quetiapine for the treatment of SUD co-

occurring with SMD in young people, we are estimating the effect size of quetiapine for the treatment of youth with co-occurring SUD and SMD based on Delbello and colleagues' preliminary report on a sample of 75 patients with frequent cannabis use and BD who were treated with quetiapine and randomized to topiramate or placebo.[49] The quetiapine plus placebo group had improvements in both substance use and mood. Cannabis use decreased from an average of 14 joints per week to 4 joints per week representing a 72% decrease. In this study, the YMRS decreased by 16 (from approximately 30 to 14) indicating a 53% improvement in mood. These expected improvements in SUD associated with mood are reminiscent of those of Geller et al using lithium for youth with SUD and SMD (effect size of ca 1.0). [20]

**Power Analysis:** To achieve 90% power using a two-tailed test with 5% significance level to detect a difference in measures of substance use we will need 22 subjects per group. To detect similarly powered differences in measures of mood we will need 10 subjects per group. Clinical trials for quetiapine in adolescents with BD have a 75 to 80% completion rate.[71, 72] We therefore estimate we may have 20% attrition and aim to recruit 28 subjects per group for a total of 56 subjects.

### 12.3 Statistical Methods

All analyses will be modified intention to treat, which will be defined by completing at least one week of study medication. We will analyze group differences across demographics using Pearson's Chi Squared tests for binary outcomes and student t tests or linear regression models for continuous outcomes. To assess our main outcomes, we will use generalized estimating equations that estimate the main effects of drug and time as well as any interactions (time X drug). We will evaluate our primary outcome measures hierarchically in the following order for SUD: Timeline Followback of substance use, urine drug screen, and Weiss craving scale. For binary outcomes, logistic regression models will be fit with Poisson family and log link, and for normally distributed data, linear regression models will be fit with the Gaussian distribution and the identity link. Exploratory aims will be examined using models similar to the main outcomes. All statistical tests will be performed using STATA 13.0. The statistical significance will be set at 5% and all tests will be two-tailed.

To evaluate hypotheses 1A, 1B and 1C, we will monitor SUD response to quetiapine for primary substance of use by way of the Timeline Followback of Substance Use (TLFB). Specifically, the TLFB will be used to compare self-report of substance for the month prior to study entry versus the last month of the study. We will use weekly toxicology screens negative for primary substance of abuse as an objective measurement of decrease in substance use severity. The Weiss Craving Scale will be used to assess the effect of quetiapine treatment on cravings for primary substance of use. Values for all three measures (TLFB, toxicology screens, and Weiss Craving Scale) will be compared between baseline and endpoint.

To evaluate hypotheses 2A and 2B, we will assess SMD response to quetiapine by way of comparing

values from baseline to endpoint on the YMRS and BDI-II.

To evaluate hypothesis 3A, the impact of treatment with quetiapine on outpatient treatment engagement will be monitored by collateral from the outpatient program regarding the percentage of scheduled appointments attended after randomization.

To evaluate exploratory aims, we plan to administer scales that measure emotional regulation, including the Emotional Control Subscale for the BRIEF (BRIEF-Self-Report, BRIEF-Adult, BRIEF-Parent, BRIEF-Informant) and the AAA subscales of the Achenbach Assessments (Youth Self-Report, Adult Self-Report, Child Behavior Checklist, Adult Behavior Checklist) to determine if they predict treatment response and/or what specific components improve with treatment in youth with co-occurring SUD and SMD. The impact of treatment with quetiapine on medication adherence will be assessed with weekly pill counts, a medication diary, and the medication adherence rating scale. Non-primary substances of use will be evaluated by TLFB and toxicology screens. Changes in high risk behaviors associated with HIV and HCV due to treatment with quetiapine will be assessed with the Risk Behavior Survey. The effect of treatment with quetiapine on functioning will be assessed by the GAF. Psychiatric co-morbidities will be assessed at baseline with specific, predetermined modules from the M.I.N.I. 7.0. Youth's reasons for substance use and peer substance use will be assessed with a supplemental substance use questionnaire at screening. Motivation to change, confidence in their ability to change, level of engagement in therapy, and exposure to substance use in the subject's living environment will be assessed with additional questions added to the Weiss Craving Scale but not factored into the total score. The validity of the PHQ-9 will be evaluated by administering the instrument in conjunction with the BDI-II at Week 0 and every 2 weeks thereafter

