**Objective 4: Assess the safety and tolerability of quetiapine in youth with SUD and SMD.**

**Exploratory Objectives:**

Evaluate whether substance use and mood symptoms are related and if so, examine the nature of the relationship. Evaluate whether scales that measure SMD, the Emotional Control Subscale for the Behavior Rating Inventory of Executive Function and the Anxiety/Depression, Attention, and Aggression subscales of the Youth Self-Report or Adult Self-Report, predict treatment response and/or what specific components improve with treatment. Evaluate whether the Patient Health Questionnaire-9 is a valid measure of mood symptoms in youth with co-occurring substance use and SMD. Examine the impact of quetiapine (versus placebo) on self-reported and objective measures of non-primary substances of use. Evaluate whether differences exist in medication adherence, high risk behaviors associated with HIV and Hepatitis C, and global functioning between the active treatment and placebo groups. Examine the impact of common psychiatric co-morbidities for youth with SUD and SMD on outcome and retention in the study. Evaluate whether youth's reasons for substance use, motivation to change, and confidence in their ability to change impact response to treatment. Assess whether level of engagement in self-help and therapy impact response to treatment. Evaluate whether peer substance use and exposure to substance use in the subject's living environment impact response to treatment.

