## 4.2 Study Outcome Measures

### 4.2.1 Primary Outcome Measures

*Outcome 1:* SUD response to quetiapine for primary substance of use will be assessed by Timeline Followback of Substance Use to assess self-report of substance use, toxicology screens negative for substances for objective measurement of substance use, and the Weiss drug craving scale to assess cravings. The Timeline Followback will be used to compare self-report of substance for the month prior to study entry versus the last month of the study. Toxicology screens and the Weiss drug craving scale will compare values from baseline to endpoint.

*Outcome 2:* SMD response to quetiapine will be assessed by the YMRS and BDI-II comparing values from baseline to endpoint.

*Outcome 3:* The impact of treatment with quetiapine on outpatient treatment engagement will be monitored by collateral from the outpatient program regarding the percentage of scheduled appointments attended after randomization.

Outcome 4: An EKG will be administered at study screening to screen for cardiac risk factors that would exclude subjects from participation. A blood draw will be completed at screening and completion; approximately 30 ccs of blood will be drawn from each subject over the course of the study. Safety and tolerability of quetiapine monotherapy will be monitored by a battery of blood tests, weight measurements (to calculate Body Mass Index (BMI)), and the AIMS at baseline and endpoint to monitor for extrapyramidal symptoms. Weight, the AIMS, and urine HCG test will also be completed at midpoint. Adverse events, suicidality (C-SSRS), the CGI-S and CGI-I for SUD and SMD will be monitored at every study visit. Vital signs will be monitored at screening, midpoint and endpoint.

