Subjects will be given the contact information to reach the study investigator 24 hours a day, 7 days a week. The PI or designee will review any and all reports of adverse events. Subjects are repeatedly advised that they can discontinue participation in the study at any time.

Subjects will be monitored for adverse events at each visit and all events will be recorded. After study completion (week 8), or if a subject withdraws early from the study, subjects will be offered up to 3 free clinical follow-up visits. The first follow-up visit will be offered within 2 weeks of the last study visit. If the subject would like to continue medication after the study they will be offered the choice of quetiapine and a prescription will be sent to the pharmacy. If a subject chooses to not continue quetiapine after the study there is no need to taper when the medication is discontinued.

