#### 9.4 Medication Management

Quetiapine will be titrated to the maximum achieved dose as tolerated during the first three weeks of the trial. Dose titration phase: Study medication will be initiated at 50 mg twice daily and will be gradually up-titrated by 100 mg per day (increasing by 50 mg twice daily) to a maximum dose of 150 mg twice daily. Titration of the study medication is flexible, guided by tolerability with the option for slower, lower, or hold titration. If a participant prefers once daily dosing instead of twice daily dosing this will be allowed.

As noted earlier, safety and tolerability of quetiapine monotherapy will be monitored by a battery of blood tests (30 cc of blood drawn over the duration of the study for fasting glucose and fasting lipids, AST, ALT, Hepatitis C and HIV testing), urine tests, height and weight measurements (to calculate Body Mass Index (BMI)), and the AIMS at screening and endpoint (completion/drop visit). Weight, the AIMS, and urine HCG test will also be completed at midpoint. As previously described, weight may also be monitored at every visit if the participant's BMI at screening is between 30 and 35. If the participant has a BMI under 30 at screening, but between 30 and 35 at midpoint, we will monitor their weight for the remainder of their visits. We will ask participants to self-report their weight, and provide a scale if they do not own one at home. If their weight increases such that their BMI increases by  $\geq 1$  from their midpoint BMI, the participant will be withdrawn from the study. Adverse events, C-SSRS, and the CGI-S and CGI-I for SUD and SMD will be monitored at every study visit. Vital signs will be monitored at screening, midpoint and endpoint visits. During the final study visit an additional 4 ccs of blood will be drawn to test the quetiapine level. The quetiapine level will only be tested for subjects who were randomized to Quetiapine. Hence, blood samples will be frozen and stored until the study is complete and unblinded.

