### **10.4 Stopping Rules**

A subject will be withdrawn from the study if they:

- Develop an adverse event despite dose adjustments that is determined to be intolerable based on clinician judgment. An intolerable event is any side effect or worsening of SMD or SUD symptoms that are determined by the investigator to be excessive in severity or in duration
- Have worsening SMD or SUD symptoms (as determined by clinician judgment indicated through scores  $\geq 5$  on the CGI Global Improvement scale on two consecutive weeks) that warrants an early termination
- Have new onset of severe SUD (e.g. intravenous, intentional/unintentional overdose)
- Have unstable mental health (new onset SI/HI with intent and/or plan)
- Become incarcerated
- Demonstrate severe noncompliance with medication dosing or study procedures
- Become pregnant during the study
- Modify their psychiatric and/or non-psychiatric medications such that they would be increasing the dose of an existing medication that may prolong QTc interval
- Add a new medication that may prolong QTc interval
- Gain weight such that their BMI increases by  $\geq 1$  point if 1) their starting BMI is between 30-35 or 2) their starting BMI is  $< 30$  but BMI at midpoint is between 30-35

In case of an emergency, the investigator will be able to contact the Boston Medical Center research pharmacy for emergency unblinding 24 hours a day. The blinded information is to be broken only when knowledge of such treatment may have an impact on future treatment decisions or aid in the emergency treatment of the subject. This decision can only be made by [name] or designee. Any subject for whom the blind is broken will be discontinued from the study. If an SAE occurs, the principal investigator, [name] or designee, should be informed of the event within 24 hours so appropriate actions may be taken.

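### The one-week completer set in Section 12.3 covers every analysis with no exception for safety Outcome 4, so a by-arm safety summary made under it would omit dosed subjects who stop in week 1

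*Combined protocol and SAP*

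**What the plan says.** Section 12.3 (Statistical Methods) opens with one population rule: "All analyses will be modified intention to treat, which will be defined by completing at least one week of study medication". The sentence is not confined to efficacy, and no other analysis set appears in the supplied text.

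Section 4.1 lists Objective 4 under the primary objectives: "Assess the safety and tolerability of quetiapine in youth with SUD and SMD". Section 4.2.1 places the matching Outcome 4 among the primary outcome measures: "Safety and tolerability of quetiapine monotherapy will be monitored by a battery of blood tests, weight measurements". That outcome also takes in the AIMS, vital signs, adverse events, the C-SSRS and the CGI scales.

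Section 12.1 states hypotheses for Aims 1 to 3 only. Section 12.3 gives methods for those aims, for demographics and for the exploratory aims. Neither says how Outcome 4 will be analysed.

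On collection, Section 6.1 says: "Subjects will be monitored for adverse events at each visit and all events will be recorded".

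**The concern.** The rule selects subjects on something that happens after randomisation and that the drug may cause. A subject who takes quetiapine for three days and stops because of it leaves both the numerator and the denominator. For a tolerability outcome, that subject is one of the events to be counted.

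Nothing in the plan prevents an exit in week 1. The intolerance rule in Section 10.4 applies when subjects "Develop an adverse event despite dose adjustments that is determined to be intolerable based on clinician judgment", and Section 9.4 makes titration flexible, "with the option for slower, lower, or hold titration". Some early side effects will therefore lead to a dose change before any withdrawal. Other exits need no prior dose change. Section 10.4 withdraws a subject with new suicidal or homicidal ideation with intent or plan, and Section 6.1 tells subjects that "they can discontinue participation in the study at any time".

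At stake is the by-arm tolerability comparison in the trial's results. With 28 subjects planned per arm, one omitted serious event or withdrawal is visible in the table.

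**Working it through.** **1. Is there an exception anywhere?**

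| Place | What it covers | Defines a population for reported safety results? |
|---|---|---|
| Section 12.3 | All analyses, one-week completers | Yes, the one-week set, by default |
| Sections 12.1–12.3 | Aims 1–3, demographics, exploratory aims | No separate set for Outcome 4 |
| Section 6.1 | Events recorded at each visit | No |
| Section 10.2 | Investigator review of serious events within 24 hours; unblinded data to the DSMB | No |
| Section 10.3 | Summaries to the IRB | No |

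No exception was found. The DSMB Charter and Data Management Plan are listed in Section 15 but were not supplied, so they could not be checked.

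**2. The denominator.** Section 12.2 needs 22 per group for substance use and allows 20% attrition: 22 / (1 − 0.20) = 27.5, rounded up to 28 per arm, 56 in total. The planned figure reproduces and is not in dispute.

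**3. Expected effect on the reported difference.** The documents give no intolerance rate and no timing, so the inputs here are assumptions. Let p be the proportion withdrawn for intolerance and s the share of those withdrawals falling in week 1. For simplicity, only these withdrawals are removed.

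- Rate in all dosed subjects: p
- Rate in the one-week set: p(1 − s) / (1 − ps)

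With even timing over 8 weeks, s = 1/8 = 0.125. For p = 0.10, 0.10 × 0.875 / (1 − 0.0125) = 0.0886. For p = 0.03, 0.03 × 0.875 / (1 − 0.00375) = 0.0263. The difference is 6.2 points, against 7.0 in all dosed subjects.

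| Quetiapine v placebo | All dosed | One-week set, s = 0.125 | Loss | Loss if s = 0.25 |
|---|---|---|---|---|
| 10% v 3% | 7.0 points | 6.2 | 11.1% | 22.5% |
| 10% v 5% | 5.0 | 4.5 | 10.8% | 22.1% |
| 15% v 5% | 10.0 | 9.0 | 10.3% | 21.1% |
| 20% v 5% | 15.0 | 13.5 | 9.7% | 20.1% |

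If s = 0, the loss is zero.

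**4. Chance that at least one quetiapine intolerance withdrawal is omitted**, with 28 per arm and s = 0.125: 1 − (1 − ps)^28.

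- p = 0.10: 1 − 0.9875^28 = 30%
- p = 0.15: 1 − 0.98125^28 = 41%
- p = 0.20: 1 − 0.975^28 = 51%

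**5. Single-trial counts** (illustrative; Newcombe 95% intervals).

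| Case | Quetiapine v placebo | Difference in points (95% CI) |
|---|---|---|
| All dosed | 4/28 v 1/28 | 10.7 (−5.8 to 28.2) |
| One quetiapine withdrawal in week 1 | 3/27 v 1/28 | 7.5 (−8.4 to 24.7) |
| The placebo withdrawal also in week 1 | 3/27 v 0/27 | 11.1 (−3.3 to 28.1) |

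A single serious event on quetiapine that ended treatment in week 1 would go from 1/28 to 0/27. The intervals overlap heavily. What changes is the reported estimate and the event listing, not a test result.

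**The case against.** **The rule may be meant for efficacy only.** Section 12 describes analyses of Aims 1 to 3 and the exploratory aims, Outcome 4 is described as monitored, and safety has its own Section 10. Read in place, the opening sentence could mean the analyses that Section 12 goes on to describe. That reading is possible, but the text does not state it, and an analyst reporting Outcome 4 has no other set to use. It is also true that no by-arm safety analysis is specified at all, so the point is conditional on one being made.

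**An unseen appendix may define a safety set.** This cannot be ruled out. Even so, Section 12.3 would need an exception for the two documents to agree plainly.

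**The size is assumed.** This stands. At 20% intolerance withdrawal, the quetiapine arm would use up the plan's whole 20% attrition allowance, so that row is at the edge of what the plan expects. The titration options reduce early withdrawals, and the exit for worsening on the CGI needs two consecutive weeks. A subject taken off at the week 1 visit may already have completed a week and be retained.

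**Much of Outcome 4 is hardly touched.** This also stands. Weight and the AIMS are next scheduled at midpoint and blood tests at completion, so unless a drop visit takes place a week-1 stopper has no later value in any set.

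**Surveillance is intact.** A reader might infer that week-1 harms would go unseen. The documents do not support that: events are recorded at each visit, the investigator reviews serious events, the DSMB receives unblinded data and the IRB receives summaries.

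**Conclusion.** The point holds. Applied as written, the population rule removes dosed week-1 stoppers from any by-arm summary of a listed primary outcome, and the removal depends on an early bad outcome. The figures affected are adverse events, the C-SSRS and withdrawals.

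The size is unknown. Under the assumed rates and even timing, the expected understatement is about 10–11% of the difference in intolerance withdrawal. It is about 20–23% if a quarter of those withdrawals fall in week 1, and nil if none do.

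A reader might go further and infer that quetiapine is bound to look better tolerated than it is. The documents do not support that: they give no week-1 rates, and the third row of counts in the check moves the other way.

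Label: wrong as written, low to moderate severity. Intact monitoring and the unknown size keep it from ranking higher.

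**What to change.** Make two changes in Section 12.3.

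1. Begin the population sentence: *All analyses except those of safety and tolerability (Outcome 4) will be modified intention to treat*, and keep the one-week definition. Wording the change as an exception, rather than limiting the rule to efficacy, leaves the demographic and exploratory analyses with a defined set.
2. Add: *Outcome 4 (adverse events, SAEs, withdrawal for intolerance, C-SSRS, and labs, weight/BMI, AIMS and vital signs where a post-baseline value exists) will be summarised by treatment received in all randomised subjects who took at least one dose; subjects dispensed drug whose dosing cannot be ruled out are included.*

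The last clause is needed because, under Section 8, drug is mailed, pills are counted at visits, and unused drug is returned only at weeks 4 and 8. A subject lost before the week 1 visit may have no count to confirm dosing.

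The cost is one amended sentence and one new one. No new data are needed and the planned 56 subjects do not change. The downside is that tolerability may look slightly worse. If the DSMB Charter or Data Management Plan already defines a safety set, the new sentence should be aligned with it.
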